5.2 Recordings. Does the research involve creating audio or video recordings?

No → If no, go to [question 5.3.](#)

Yes → If yes, verify that you have described what will be recorded in 5.1 and answer question a.

a. Before recording, will consent for being recorded be obtained from subjects and any other individuals who may be recorded?

No → If no, email [contact] before submitting this application in Zipline. In the email, include a brief description of the research and a note that individuals will be recorded without their advance consent.

Yes

5.3 MRI scans. Will any subjects have a Magnetic Resonance Imaging (MRI) scan as part of the study procedures?

This means scans that are performed solely for research purposes or clinical scans that are modified for research purposes (for example, using a gadolinium-based contrast agent when it is not required for clinical reasons).

→ If no, go to [question 5.4](#).

→ If yes, answer questions a through c.

a. Describe the MRI scan(s). Specifically:

- What is the purpose of the scan(s)? *Examples: obtain research data; safety assessment associated with a research procedure.*
- Which subjects will receive an MRI scan?
- Describe the minimum and maximum number of scans per subject, and over what time period the scans will occur. *For example: all subjects will undergo two MRI scans, six months apart.*

b. MRI facility. At which facility(ies) will the MRI scans occur? Check all that apply.

UWMC Radiology/Imaging Services (the UWMC clinical facility)
 DISC Diagnostic Imaging Sciences Center (UWMC research facility)
 CHN Center for Human Neuroscience MRI Center (Arts & Sciences research facility)
 BMIC Biomolecular Imaging Center (South Lake Union research facility)
 Harborview Radiology/Imaging Services (the Harborview clinical facility)
 SCCA Imaging Services
 Northwest Diagnostic Imaging
 Other: identify in the text box below:

c. Personnel. For MRI scans that will be conducted at the DISC, CHN or BMIC research facilities: Indicate who will be responsible for operating the MRI scanner by checking all that apply.

MRI technician who is formally qualified
 Researcher who has completed scanner operator training provided by a qualified MRI operator

5.4 Data variables. Describe the specific data that will be obtained (including a description of the most sensitive items). Alternatively, a list of the data variables may be uploaded to [Zipline](#).

These examples are of the most sensitive and risky questions we may ask. None of the measures are intended to capture information on suicidality or some other condition that would need referral or notification to some other entity. Please note the follow-up assessment are about 10 minutes shorter as we will not be collecting any lifetime behaviors questions.

Alcohol, Tobacco and Other Drug Use.

Current alcohol use. Participants will be asked if they drank alcohol in the past 30 days

Problem drinking, GAINS Short Screener for youth

ATOD Age initiation. Age of first alcohol, tobacco, marijuana and other drug use.

Peer Alcohol Associations. Number of friends that drink often, peer encouragement to drink or get drunk.⁴²

Susceptibility to initiate ATOD among self-reported non-smokers, non-drinkers, and non-drug users we will ask 6 questions on a 4-point scale: (eg. "if one of your best friends offered you a cigarette/joint/drink, would you smoke it?").

Specific Event Drug and Alcohol Refusal Efficacy scale (SEDARE) perceived likelihood that youth will use drugs and alcohol in specific situations and inquires whether the respondent would be tempted to use alcohol or marijuana in eight potentially stressful or pressured situations.⁴³

Non-ceremonial tobacco use. Adapted from the NSDUH include current cigarette use, vaping and juuling.

Adolescent Sexual and Reproductive Health.

Sexual activity. Adolescent Sexual Risk Behavior 11-item and Adolescent Sexual Activity Index (ASAI) 10 items assess current and past sexual practices with most items focused on pre-coital behaviors during last 12 months for the sexual activities with other youth. If yes to pre-coital behaviors additional items assess if they have engaged in sexual intercourse, frequency, frequency of sex without birth control, frequency of sex without a condom; number of different sexual partners; and whether or not alcohol or drugs were used at first sex experience and/or last time had sex.

Safer sex intentions. Health Belief Model-Intentions for Safer Sex (HBMI) 7-item/5 pt scale (e.g., "I do not plan on having sex until I am at least 18 years old").

Predictors, Mediators, and Moderators. Spirituality (*Native American Spirituality Scale, Traditional Spiritual Activities scale*)

Standard measures:

Mental health/well-being (e.g., self-esteem, GAD-7, and PHQ-8) for youth and culturally-specific stressors such as familial historical trauma, microaggressions, in-community microaggressions.

Community Values Scale, level of internalization of AIAN collective values related to traditionalism and benevolence.

Hemingway Measure of Adolescent Connectedness.⁴⁵ Positive Youth Development-related moderators.

5.5 Data sources. For all types of data that will be accessed or collected for this research: Identify whether the data are being obtained from the subjects (or subjects' specimens) or whether they are being obtained from some other source (and identify the source).

If you have already provided this information in Question 5.1, you do not need to repeat the information here.

All data collected will be from youth participants via the online survey

5.6 Identifiability of data and specimens. Answer these questions carefully and completely. This will allow HSD to accurately determine the type of review that is required and the relevant compliance requirements. Review the following definitions before answering the questions:

Access means to view or perceive data, but not to possess or record it. See, in contrast, the definition of "obtain".

Identifiable means that the identity of an individual is or may be readily (1) ascertained by the researcher or any other member of the study team from specific data variables or from a combination of data variables, or (2) associated with the information.

Direct identifiers are direct links between a subject and data/specimens. Examples include (but are not limited to): name, date of birth, medical record number, email or IP address, pathology or surgery accession number, student number, or a collection of data that is (when taken together) identifiable.

Indirect identifiers are information that links between direct identifiers and data/specimens. Examples: a subject code or pseudonym.

Key refers to a single place where direct identifiers and indirect identifiers are linked together so that, for example, coded data can be identified as relating to a specific person. Example: a master list that contains the data code and the identifiers linked to the codes.

Obtain means to possess or record in any fashion (writing, electronic document, video, email, voice recording, etc.) for research purposes and to retain for any length of time. This is different from **accessing**, which means to view or perceive data.

a. Will you or any members of your team have access to any direct or indirect identifiers?

X

→ If yes, describe which identifiers and for which data/specimens.

[REDACTED] will have access to students' names, email address, and phone numbers so they can engage students in the intervention.

UW staff will have access to names, email address, and phone numbers and the link file so they can conduct longitudinal data collection.

1

→ If no, select the reason(s) why you (and all members of your team) will not have access to direct or indirect identifiers.

There will be no identifiers.

Identifiers or the key have been (or will have been) destroyed before access.

There is an agreement with the holder of the identifiers (or key) that prohibits the release of the identifiers (or key) to study team members under any circumstances.

This agreement should be available upon request from the IRB. Examples: a Data Use Agreement, Repository Gatekeeping form, or documented email.

- There are written policies and procedures for the repository/database/data management center that prohibit the release of the identifiers (or identifying link). This includes situations involving an Honest Broker.

There are other legal requirements prohibiting the release of the identifiers or key. Describe them below.

b. Will you or any study team members obtain any direct or indirect identifiers?

Yes

→ If yes, describe which identifiers and for which data/specimens.

students' names, email address, and phone numbers so students can engage in the intervention.

No

→ If no, select the reason(s) why you (and all members of your team) will not obtain direct or indirect identifiers.

There will be no identifiers.

Identifiers or the key have been (or will have been) destroyed before access.

There will be an agreement with the holder of the identifiers (or key) that prohibits the release of the identifiers (or key) under any circumstances.

This agreement should be available upon request from the IRB. Examples: a Data Use Agreement, Repository Gatekeeping form, or documented email.

There are written policies and procedures for the repository/database/data management center that prohibit the release of the identifiers (or identifying link). This includes situations involving an Honest Broker.

There are other legal requirements prohibiting the release of the identifiers or key. Describe them below.

c. If any identifiers will be obtained, indicate how the identifiers will be stored (and for which data). NOTE: Do not describe the data security plan here – that information is requested in section 9.6.

Identifiers will be stored with the data. Describe the data to which this applies:

Identifiers and study data will be stored separately but a link will be maintained between the identifiers and the study data (for example, through the use of a code). Describe the data to which this applies:

Identifiers will be stored on a password protected Excel file on a password protected computer.

Only UW research staff will facilitate data collection. The only connection between students' research data (assessments) and identifiers is a unique code stored on one file, on a secured server, password protected file.

Identifiers and study data will be stored separately, with no link between the identifiers and the study data. Describe the data to which this applies:

d. Research collaboration. Will individuals who provide coded information or specimens for the research also collaborate on other activities for this research? If yes, identify the activities and provide the name of the collaborator's institution/organization.

Examples include but are not limited to: (1) study, interpretation, or analysis of the data that results from the coded information or specimens; and (2) authorship on presentations or manuscripts related to this work.

no

5.7 Protected Health Information (PHI). Will participants' identifiable PHI be accessed, obtained, used, or disclosed for any reason (for example, to identify or screen potential subjects, to obtain study data or specimens, for study follow-up) that does not involve the creation or obtaining of a Limited Data Set?

PHI is individually identifiable healthcare record information or clinical specimens from an organization considered a "covered entity" by federal HIPAA regulations, in any form or media, whether electronic, paper, or oral. You must answer yes to this question if the research involves identifiable health care records (e.g., medical, dental, pharmacy, nursing, billing, etc.), identifiable healthcare information from a clinical department repository, or observations or recordings of clinical interactions.

No

→ If no, skip the rest of this question; [go to question 5.8](#)

Yes

→ If yes, answer all of the questions below.

a. Describe the PHI and the reason for using it. *Be specific. For example, will any "free text" fields (such as physician notes) be accessed, obtained, or used?*

b. Is any of the PHI located in Washington State?

No

Yes

c. Describe the pathway of how the PHI will be accessed or obtained, starting with the source/location and then describing the system/path/mechanism by which it will be identified, accessed, and copied for the research. *Be specific. For example: directly view records; search through a department's clinical database; submit a request to Leaf.*

d. For which PHI will subjects provide HIPAA authorization before the PHI is accessed, obtained and/or used?

Confirm by checking the box that the UW Medicine [HIPAA Authorization](#) form maintained on the HSD website will be used to access, obtain, use, or disclose any UW Medicine PHI.

Confirmed

e. For which PHI will HIPAA authorization NOT be obtained from the subjects?

Provide the following assurances by checking the boxes.

The minimum necessary amount of PHI to accomplish the purposes described in this application will be accessed, obtained and/or used.

The PHI will not be reused or disclosed to any other person or entity, except as required by law, for authorized oversight of the research study, or for other research for which the use or disclosure of PHI would be permitted.

The HIPAA “accounting for disclosures” requirement will be fulfilled, if applicable. See [UW Medicine Compliance Policy #104](#).

There will be reasonable safeguards to protect against identifying, directly or indirectly, any patient in any report of the research.

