"Minimal risk" means that the probability and magnitude of harm or discomfort anticipated in the research are not greater than those ordinarily encountered in daily life or during the performance of routine physical or psychological examinations or tests.

a. **Background.** Provide the rationale and the scientific or scholarly background for the proposed activity, based on existing literature (or clinical knowledge). Describe the gaps in current knowledge that the project is intended to address.

This should be a plain language description. Do not provide scholarly citations. Limit your answer to less than one page, or refer to an attached document with background information that is no more than three pages long.

Study is a phase 2 clinical trial.

Evidence shows that Native Americans have high rates of substance use disorder (ATOD) over the lifetime and die at higher rates than non-Natives from ATOD-related diseases such as cirrhosis and suicide. They also have a higher prevalence of behavioral risk factors for substance misuse and sexual health risk. **AIAN youth are at the heart of this health crisis.** AIAN youth have a lower overall mean age of tobacco use, alcohol use, and marijuana initiation (11.5 years) than the general population. Early initiation of ATOD use is associated with an array of negative physical and behavioral health outcomes including academic challenges, later ATOD abuse, and early sexual initiation. AIAN youth also have the earliest age of first sexual intercourse, and have more sexual partners than their non-AIAN counterparts. To stem the epidemic of ATOD-SRH-related health disparities among AIAN youth, collaborative partnerships must focus on development of culturally grounded, sustainable health interventions that incorporate healing related to historical trauma. In response, we will adapt and expand a promising Native-specific intervention, Discovering Our Story, **to develop the [REDACTED] Journey of Transformation (CJT) - Native Health Youth Leadership Program**, an intervention to prevent ATOD use and SRH in AIAN youth attending boarding school. If successful, this project would have high relevance for boarding and tribal day school students across the country.

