2 PARTICIPANTS

2.1 Participants. Describe the general characteristics of the subject populations or groups, including age range, gender, health status, and any other relevant characteristics.

AIAN youth, all genders (ages 13-16) attending the [REDACTED] Indian School

2.2 Inclusion and exclusion criteria.

a. Inclusion criteria. Describe the specific criteria that will be used to decide who will be included in the research from among interested or potential subjects. Define any technical terms in lay language.

Eligible youth must be:

(a) between 13 years of age and 16 years of age;
and
(b) currently attend [REDACTED] Indian School in the 9th grade.

b. Exclusion criteria. Describe the specific criteria that will be used to decide who will be excluded from the research from subjects who meet the inclusion criteria listed above. Define any technical terms in lay language.

none

2.3 Prisoners. IRB approval is required in order to include prisoners in research, even when prisoners are not an intended target population.

Is the research likely to have subjects who become prisoners while participating in the study?

For example, a longitudinal study of youth with drug problems is likely to have subjects who will be prisoners at some point during the study.

No

Document Date & Version

01/21/2021

Version 3.0

Researcher Date & Version

10/04/2022

Version 5.1

Page 8 of 56

Yes → If yes, if a subject becomes a prisoner while participating in the study, will any study procedures and/or data collection related to the subject be continued while the subject is a prisoner?

No
 Yes

→ If yes, describe the procedures and/or data collection that will continue with prisoner subjects

2.4 Will the proposed research recruit or obtain data from individuals that are known to be prisoners?

For records reviews: if the records do not indicate prisoner status and prisoners are not a target population, select "No". See the [WORKSHEET Prisoners](#) for the definition of "prisoner".

No
 Yes

→ If yes, answer the following questions (i – iv).

i. Describe the type of prisoners, and which prisons/jails:

ii. One concern about prisoner research is whether the effect of participation on prisoners' general living conditions, medical care, quality of food, amenities, and/or opportunity for earnings in prison will be so great that it will make it difficult for prisoners to adequately consider the research risks. How will the chances of this be reduced?

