All freshmen (9th grade) students at [REDACTED] are American Indian or Alaska Native and between the ages of age of 13 and 16. Thus, by school administration assignment into the 9th grade student meet the recruitment criteria.

4.2 Recruitment materials.

a. What materials (if any) will be used to recruit and screen subjects?

Examples: talking points for phone or in-person conversations; video or audio presentations; websites; social media messages; written materials such as letters, flyers for posting, brochures, or printed advertisements; questionnaires filled out by potential subjects.

Flyer

Study Website content

Class presentation talking points

Zoom Meetings talking points

We request flexibility to make minor revisions to our recruitment materials without submitting modifications to the IRB. If the revisions go outside the range and scope of approved materials and topics, we will submit a modification

b. Upload descriptions of each type of material (or the materials themselves) to **Zipline**. If letters or emails will be sent to any subjects, these should include a statement about how the subject's name and contact information were obtained. No sensitive information about the person (such as a diagnosis of a medical condition) should be included in the letter.

HSD encourages researchers to consider uploading descriptions of most recruitment and screening materials instead of the materials themselves. The goal is to provide the researchers with the flexibility to change some information on the materials without submitting a Modification for IRB approval of the changes. Examples:

- *Provide a list of talking points that will be used for phone or in-person conversations instead of a script.*
- *For the description of a flyer, include the information that it will provide the study phone number and the name of a study contact person (without providing the actual phone number or name). This means that a Modification would not be necessary if/when the study phone number or contact person changes. Also, instead of listing the inclusion/exclusion criteria, the description below might state that the flyer will list one or a few of the major inclusion/exclusion criteria.*
- *For the description of a video or a website, include a description of the possible visual elements and a list of the content (e.g., study phone number; study contact person; top three inclusion/exclusion criteria; payment of \$50; study name; UW researcher).*

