Journey of Transformation Curriculum for Native American Adolescents (JOT)

NCT05274217

[name]

Statistical Analysis Plan

IRB Approved 03-16-2021

Statistical Design and Power

This study will evaluate the following primary outcomes: (1) alcohol, tobacco, and other drugs (ATOD; intentions to use, overall use, susceptibility, refusal self-efficacy) and (2) sexual and reproductive health (sexual activity, sexual self-efficacy, safer sex intentions). An intent-to-treat approach will be used to estimate the magnitude and statistical significance of intervention effects at immediate post-intervention. Each outcome will be evaluated in a separate generalized linear mixed model to evaluate the effect of CHJOT curriculum on intervention outcomes. Continuous outcomes will be modeled using a Gaussian link function for normally distributed data and binary outcomes using a logit link for Bernoulli-distributed data. The following equation represents the basic model for the outcomes: $Outcome_{tij} = b_0 + b_1 Intervention_i + b_2 Time + b_3 (Intervention_{ij} \times Time_{tij}) + u_{0i} + r_{0ij} + e_{tij}$, where t indexes assessment, i indexes individual, and j indexes classroom. The last three terms on the right side of the model equation represent the variability between classrooms (u_{0i}), between individuals within classroom (r_{0ij}), and residual error (e_{tij}), respectively. The statistical test of the CHJOT curriculum will be the Intervention by Time interaction, which will evaluate whether recipients of the intervention curriculum improved more or decreased less from pre- to 2-month post-intervention compared with waitlist control.

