To estimate the necessary sample size for our Longitudinal Mediation Model. We assume 80% power to detect a small intervention effect of $d = 0.22$ (standardized mean effect) of CJT (immediate intervention) vs. Waitlist control in pre-intervention to 3 month post-intervention outcome change. We base our power analysis on a repeated measures ANOVA design evaluating the Intervention by Time interaction in the primary outcome analysis, assuming a Type I error rate of 5%. Assuming a moderate temporal stability ($r = .25$) of the outcome measures, which is reasonable given the short interval between assessments, post-baseline data from 255 participants will be necessary to detect an intervention effect equivalent to a Cohen's d as low as 0.20, which would accommodate a 10% reduction in the observed intervention effect due to potential early exposure of control participants to the intervention (i.e., contamination effects). We anticipate a modest attrition rate of 15%, as the intervention will be offered in a required class in a boarding school indicating an analytic sample of 216 participants. Thus, our planned recruitment of 255 participants will provide a sufficient sample to detect targeted intervention effect, after accounting for attrition.

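### Susceptibility is a primary intent-to-treat outcome, but its items go only to self-reported non-users, so it cannot be compared in all randomised students

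*Protocol*

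**What the plan says.** The SAP (Statistical Design and Power) lists among its primary outcomes "alcohol, tobacco, and other drugs (ATOD; intentions to use, overall use, susceptibility, refusal self-efficacy". It continues: "An intent-to-treat approach will be used to estimate the magnitude and statistical significance of intervention effects at immediate post-intervention". Each outcome gets its own mixed model and is tested by the Intervention by Time term. No outcome is given a restricted population. The power paragraph covers all of them with one figure, "indicating an analytic sample of 216 participants".

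Protocol 5.4 describes the measure: "Susceptibility to initiate ATOD among self-reported non-smokers, non-drinkers, and non-drug users we will ask 6 questions on a 4-point scale". It also says of the later surveys: "the follow-up assessment are about 10 minutes shorter as we will not be collecting any lifetime behaviors questions".

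Eligibility does not depend on substance use. Protocol 2.2 asks for 9th graders "between 13 years of age and 16 years of age" and lists no exclusions. Protocol 4.1 concludes: "Thus, by school administration assignment into the 9th grade student meet the recruitment criteria". The objectives in Protocol 1.5 include lowering rates of use, and in Protocol 5.1 the mentor goals cover cutting down as well as avoiding use. Both presuppose that some enrolled students already use.

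**The concern.** A student who is never asked the items has no susceptibility score at any survey and contributes nothing to that model. The analysis the SAP describes, all students as randomised, therefore does not exist for this outcome. What can be estimated is an effect among non-users, and the SAP does not say so.

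Three things are left open:

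- whether a non-user is someone who has never used or someone not using now;
- whether a user of one substance still answers about the others;
- whether the filter is set once or applied at each survey.

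The third matters most. If the filter is applied again, use after randomisation decides who has a post-intervention score. Overall use is itself a primary outcome that the programme is meant to change. Students who start using drop out of the susceptibility comparison, and they are probably the more susceptible ones. A programme that prevents first use would keep more of them in its own arm and look less effective on this measure.

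With no named population, the choice could also be made after the data are seen, and a non-user result could be reported as an effect in all randomised students.

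**Working it through.** **1. The plan's own figure.** The attrition step reproduces: 255 x 0.85 = 216.75, and 216 / 0.85 rounds up to 255. The sample size itself does not. For a two-group, two-time repeated-measures ANOVA, take f = d/2 and noncentrality = f^2 x 2 x N / (1 - r), with r = .25 and two-sided 5% (sidedness is not stated). Then 80% power needs N = 246 for d = 0.22 and N = 297 for d = 0.20. At N = 216 the power is 0.748 and 0.666. That mismatch is a separate matter; it means only that 80% should not be taken as the starting power at 216.

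**2. Users have no score.** The share of users at baseline is not in the documents; 10-40% is assumed. Analysed students = 216 x (1 - share). The detectable effect is multiplied by 1/sqrt(1 - share). Power comes from the formula in step 1.

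| Users (assumed) | Analysed | Detectable effect | Power, d = 0.22 | Power, d = 0.20 |
|---|---|---|---|---|
| 0% | 216 | x 1.00 | 0.748 | 0.666 |
| 10% | 194 | x 1.05 | 0.702 | 0.619 |
| 20% | 173 | x 1.12 | 0.652 | 0.570 |
| 30% | 151 | x 1.20 | 0.592 | 0.513 |
| 40% | 130 | x 1.29 | 0.529 | 0.455 |

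The absolute powers depend on how d is read. If it is the difference in mean change in raw-SD units, a change-score test needs 974 students for d = 0.22, and power at 216 is 0.261. The multiplier in the third column does not depend on that reading.

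**3. If the filter is applied again at follow-up.** This is conditional, because the documents do not say. The simulation used 1,000,000 baseline non-users per arm, standardised scores with r = .25, the Week 9 score missing for students who start, and a likelihood-based mixed-model estimate of arm by time using all baseline scores. Starting by Week 9 was assumed at 2-10% of controls. Over 8 weeks that is 1 - (1 - q)^6.5 a year, or 12% to 50%.

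- Starting tied to the Week 9 score (logit slope 1 to 2 per SD): a true benefit of 0.20 SD shrinks by 1.5-14%.
- Starting tied to the average of the baseline and Week 9 scores: it shrinks by about 1-6%.
- Starting tied to the baseline score only: about zero.
- Programme halves starting but does not change susceptibility (starting tied to the Week 9 score): a spurious harm of about 0.01-0.07 SD.

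The shrinkage figures carry simulation error of roughly one to two percentage points. The first and last cases are the upper end of the mechanisms considered, because they tie starting before Week 9 to the score measured at Week 9.

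**4. What a repeated filter would rest on.** Lifetime questions are dropped after baseline. A repeated filter would therefore have to use current-use answers or carry baseline status forward. Under the first, a baseline user who has stopped could enter at follow-up with no baseline score, while a baseline non-user who has started would leave.

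**The case against.** The strongest reply is that the measure concerns susceptibility to initiate. Initiation has meaning only for students who have not started, so asking non-users follows from the construct, and the measure's description states its own population. This stands. Baseline non-users analysed as assigned are a valid randomised subgroup, and users still count in the other ATOD outcomes. It does not answer the concern, because the SAP declares intent-to-treat without naming that subgroup and uses one sample size for everything.

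A second reply is that Protocol 5.4 calls its list examples. That is fair. Protocol 5.14 says the survey will consist of the 5.4 items, yet 5.4 contains no item on intentions to use substances or on sexual self-efficacy, both primary in the SAP, so 5.4 is probably not the whole survey. Inferences from its silence are weak, but the explicit restriction on the susceptibility items is unaffected.

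Three stronger readings are tempting, and the documents do not support them:

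- **That the filter is applied at each survey and the result is therefore biased.** The wording allows this, but no text says it.
- **That most enrolled students are users.** Protocol 1.8 says "AIAN youth have a lower overall mean age of tobacco use, alcohol use, and marijuana initiation (11.5 years) than the general population". A mean age at starting describes those who started, not how many did. The better evidence that some users are expected is the aim of reducing use.
- **That every student must be asked the items.** In users they measure willingness to use, so an all-student score mixes two constructs. Protocol 5.4 also lists a refusal-efficacy scale, with no user filter, that covers temptation in pressured situations.

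**Conclusion.** The point holds in a limited form. As written, the susceptibility outcome cannot be compared in all randomised students, and 216 is not its sample size. That rests on explicit text in both documents plus the inference, from open eligibility and the reduction aims, that some students use at baseline.

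The loss is 10-40% of the analysed sample and a detectable effect 5-29% larger, on an assumed share of users. The possible bias is a second, conditional problem: it arises only if the filter is applied again and starting is related to susceptibility at follow-up. Its size is then probably modest.

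This affects one of seven listed primary outcomes and does not undermine the others. It is worth fixing because the repair is cheap, and because a susceptibility score not collected from a student who has since started using cannot be recovered later.

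**What to change.** 1. Set non-user status once, at baseline, and define it: never or not currently, and any substance or each one separately.
2. Ask the six items of all baseline non-users at every later survey, whatever their use by then. Do not apply the filter again.
3. In the SAP, name baseline non-users, analysed as assigned, as the population for susceptibility, and state that its sample and power are lower than for the other outcomes.
4. Asking users as well is optional. If done, report the all-student result and the non-user result separately.

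The cost is a small change of skip logic, a few SAP sentences and an IRB modification. Protocol 4.4 shows that the baseline survey has already been fielded once, so this revises an existing form. The students described there take no further surveys, so none of them would meet two versions.
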